### **Compliance with the Protocol**

The study shall be conducted as described in this approved protocol. All revisions to the protocol must be discussed with, and be prepared by the study team.

## GLOSSARY OF TERMS

Term	Definition
Adverse Reaction	An adverse event that is considered by either the investigator or the sponsor to be related to the investigational product.
Expedited Safety Report	Rapid notification to investigators of all SAEs that are suspected (related to the investigational product) and unexpected (ie, not previously described in the Investigator Brochure), or that could be associated with the study procedures.
Hemostasis	Defined by no further ooze from groin puncture sites after pressure hold is released. Typically, 3-4 hours post procedure.
SUSAR	Suspected, Unexpected, Serious Adverse Reaction as termed by the European Clinical Trial Directive (2001/20/EC).
Unexpected Adverse Reaction	An adverse reaction, the nature or severity of which is not consistent with the applicable product information (eg, Investigator Brochure for an unapproved investigational product).
Peri-Procedural Bleeding	Occurring prior to the procedure within 48 hours and up to 48 hours post procedure.
Recent MI	Recent is defined as within 30 days of the planned procedure.

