##### **Secondary Objectives:**

- To estimate the impact of DOAC on major peri-procedural bleeding in patients undergoing left ventricular arrhythmia ablation when compared to ASA. Assessment done up to 30 days post procedure.
- To estimate the impact of DOAC on minor peri-procedural bleeding in patients undergoing left ventricular arrhythmia ablation when compared to ASA. Assessments completed at 1 week post procedure and up to 30 days post procedure.

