### Primary End Point Assessment

Incidence of periprocedural embolic events –TIA/CVA/other systemic embolic events immediately after the left ventricular arrhythmia ablation up to 30 days post left ventricular arrhythmia ablation.

The incidence of new asymptomatic cerebrovascular events as documented by MRI at 24-48 hours post procedure and at 30 days after the left ventricular arrhythmia ablation.

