### Secondary End Point Assessments

- A. Major bleeding events as defined above using TIMI criteria
- B. Minor Bleeding events as defined by the TIMI criteria

- C. Cardiovascular mortality
- D. All-Cause mortality
- E. Any other adverse events occurring during the study period

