### **DATA MONITORING COMMITTEE**

To meet the study's ethical responsibility to its subjects, an independent data safety monitoring Board (DSMB) will monitor results during the study. The board consists of 2 physicians and 1 statistician who have no formal involvement or conflict of interest with the subjects or the investigators. Records will be reviewed after the first 50 patients and then at the completion of the study.

If the major bleeding events in the DOAC group occur at >15% but <30% (absolute event rate) of those in the ASA group during any of the assessments, a recommendation will be made to consider modifying the study by the members of the DSMB. First consideration to modify is to decrease the dose of the drug to 2.5mg PO twice daily. If the major bleeding events in the DOAC group occur at >30% (absolute event rate) of those in the ASA group during any of the assessments, a recommendation will be made to stop the study by the members of the DSMB.

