### **STATISTICAL CONSIDERATIONS**

#### ***Study Management and Sample Size Justification***

This is a pilot study and 52 total patients will be enrolled in the study. We expect to analyze a total of 50 patients and each arm will consist of 25 patients. The additional 2 allows for attrition. Since this is a pilot study, the number needed to treat to achieve a pre-specified statistical significance cannot be calculated accurately. Exact sample size could not be given due to lack of pre-existing data on this subject. We hypothesize a 30% difference in outcomes can be seen with a total sample size of 50 patients.

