#### **Data Collection Center**

The Kansas City Heart Rhythm Research Foundation will be the coordinating site for the study. A project manager (PM) with the help of the PI will create the study worksheets and create the CRFs. The sites will complete the paper CRF and submit via secure email to the project manager. The PM will assist the Database Manager (DM) with updating the access database and providing computer support for outside centers. All data will be submitted via secure email including de-identified patient data that is to be used as source.

Participant's data will be de-identified and a code will be assigned. The code will consist of Site Number, Patient Number and Patient Initials. The coordinator at that site will have access to the code; the linking list will be destroyed at the completion of the project.

**Statistical analysis:** Patients will be randomized in a stratified manner to control arm versus treatment arm. We will analyze the differences in secondary endpoints between the two groups for major, minor bleeding and cardiovascular mortality up to 30 days post ablation. Categorical variables will be reported as counts and percentages and continuous variables will be expressed as mean  $\pm$  SD. Continuous variables will be compared using t-test for normally distributed data or Mann Whitney U test for non-normally distributed data as deemed appropriate. Categorical events will be compared using chi-square test for parametric data.

Univariate and multi-variate analysis will be performed to identify the predictors of systemic thromboembolic events and mortality. This is a pilot study to study the feasibility and safety of the study. A larger study will be done in the future if there is a positive signal.

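### The TIMI major-bleeding definition does not fit the 30-day bleeding endpoint: its fatal clause ends at day 7, it leaves a gap at exactly 5 g/dL, and the glossary window disagrees

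*Combined protocol and SAP*

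**What the plan says.** **Window.** Both bleeding objectives under Secondary Objectives use the term peri-procedural bleeding. For major bleeding the plan adds "Assessment done up to 30 days post procedure"; for minor bleeding, "Assessments completed at 1 week post procedure and up to 30 days post procedure". The statistical analysis paragraph (under Data Collection Center) compares the arms for "major, minor bleeding and cardiovascular mortality up to 30 days post ablation". The Glossary of Terms defines peri-procedural bleeding differently: "Occurring prior to the procedure within 48 hours and up to 48 hours post procedure".

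**Grading.** Secondary End Point Assessments lists "Major bleeding events as defined above using TIMI criteria" and then minor bleeding, with no time window for either. The criteria are in the TIMI table under Safety Assessments. Major bleeding is any one of:
- symptomatic intracranial hemorrhage;
- overt hemorrhage with a hemoglobin fall above 5 g/dL (hematocrit above 15% if hemoglobin is not available);
- bleeding that directly causes death no later than 7 days after the procedure.

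Minor bleeding is overt hemorrhage with a fall from 3 to below 5 g/dL (hematocrit 9 to below 15%). Other bleeds are classed as requiring medical attention or as minimal.

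**Use of the grade.** The Data Monitoring Committee section ties its recommendations to major bleeding, again with no window: "If the major bleeding events in the DOAC group occur at >15% but <30% (absolute event rate" leads to considering a modification, and a rate above 30% leads to a recommendation to stop.

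**The concern.** The trial describes itself as a feasibility and safety pilot, with a larger study to follow if the signal is positive. Bleeding is its named safety outcome, so the rules that decide which bleeds are major should cover the same 30 days as treatment and endpoint. Two of them do not work as written.

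The fatal criterion lapses after day 7. A fatal bleed in the last three weeks must then qualify by another route, and one route needs a laboratory value that the protocol does not schedule. A death from bleeding could therefore be graded below major.

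The cut-points also put a fall of exactly 5 g/dL below a fall of 4.9 g/dL, which is the wrong order.

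The glossary row adds a third, lesser inconsistency. It gives a formal definition of a term that the objectives use with a different window.

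**Working it through.** The plan gives no figure to reproduce here. The check compares definitions and uses simple arithmetic.

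**1. Fatal clause against the endpoint window**
- Endpoint window: 30 days (Secondary Objectives; statistical analysis paragraph). Treatment: 30 days (Study Design and Duration). Fatal clause: 7 days (Safety Assessments).
- Not covered: 30 − 7 = 23 days; 23/30 = 77% of the post-procedure period.
- From day 8 to day 30 a fatal bleed is major only if it is a symptomatic intracranial hemorrhage or has a documented fall above 5 g/dL or 15%.
- The Time and Events Schedule marks laboratory tests at baseline only. A later hemoglobin value exists only if clinical care happens to measure it.
- A fatal bleed meeting neither condition would be missing from the major-bleeding endpoint and from the board's count. It would still be counted in all-cause mortality and reported as a serious adverse event.

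**2. Cut-points as the text reads**

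| Hemoglobin fall (g/dL) | Major (>5) | Minor (3 to <5) |
|---|---|---|
| 4.9 | no | yes |
| 5.0 | no | no |
| 5.1 | yes | no |

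| Hematocrit fall (%) | Major (>15) | Minor (9 to <15) |
|---|---|---|
| 14.9 | no | yes |
| 15.0 | no | no |
| 15.1 | yes | no |

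The gap is one value wide. An event in it drops to requiring medical attention or minimal, and so leaves both secondary bleeding endpoints.

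**3. Glossary against the objectives**
- Applied literally, the glossary covers 2 of the 30 post-procedure days and leaves out 30 − 2 = 28 (28/30 = 93% of the time).
- Four places point to 30 days instead: the Secondary Objectives; the statistical analysis paragraph; the Day 30 visit, which includes a TIMI evaluation; and the Primary End Point Assessment, which applies the word periprocedural to embolic events "immediately after the left ventricular arrhythmia ablation up to 30 days post left ventricular arrhythmia ablation".
- If the analysis paragraph is followed, no post-procedure bleed up to Day 30 is lost.

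**4. Weight of one regraded bleed**
- The sample-size section says "each arm will consist of 25 patients". One bleed is 1/25 = 4 percentage points.
- 3/25 = 12% and 4/25 = 16% lie on either side of the 15% limit; 7/25 = 28% and 8/25 = 32% lie on either side of the 30% limit. This assumes that the board's percentages are an absolute rate, or an absolute difference between equal arms; the wording is not clear.
- The board first reviews after 50 patients, and 52 are to be enrolled: 50/52 = 96%. At most 2 further enrolments remain, plus anyone still within the 30 days of treatment.

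**5. One-week assessment**
- The minor-bleeding objective names an assessment at 1 week. The Time and Events Schedule and the visit lists contain no such visit.

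**The case against.** The strongest reply is that little of this changes a result.

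- **Glossary.** Each objective that uses the term states its own 30-day window, and neither the analysis paragraph, the endpoint list nor the board's rule uses the glossary term. This stands. A reader might infer that 93% of the follow-up time is lost to the endpoint; the documents do not support that, because the Secondary Objectives and the analysis paragraph override the glossary row. A reader might also infer that bleeds before randomization would be counted. That needs a literal glossary reading, an inferred unit in the schedule's randomization column (which says only 48) and a bleed already resolved, since active bleeding is an exclusion.
- **Cut-point gap.** It touches very few bleeds. The table was read from PDF by a program, so an 'or equal' sign may have been lost. An event in the gap that needed medical attention would still be in the TIMI table's clinically significant composite. All of this stands, though that composite is not in the list of secondary endpoints.
- **Fatal clause.** The 7-day limit is explicit, and no sentence directly contradicts it. The missed case needs a fatal bleed after day 7, no symptomatic intracranial hemorrhage and no documented fall, and it would still appear as a death and as a serious adverse event. This limits the size. It does not remove the mismatch with a 30-day endpoint, because a fatal bleed could still be absent from the count of major bleeds.
- **Monitoring rule.** A reader might infer from the 3-versus-4 and 7-versus-8 examples that the stopping rule is seriously weakened. The documents do not support that. The first review comes after 50 of 52 patients, the board issues recommendations, and the arm would have to sit one bleed below a limit with that one bleed being among these rare cases.

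**Conclusion.** The point holds as a defect in endpoint wording. In order of weight:

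1. The fatal clause leaves days 8 to 30 uncovered in a 30-day endpoint. With no scheduled post-procedure laboratory test, a fatal bleed in that period could be missed by the major-bleeding endpoint and the board's count, though not by all-cause mortality or serious adverse event reporting.
2. As the text reads, a fall of exactly 5 g/dL or 15% is neither major nor minor. Few bleeds are affected, and this rests on the printed signs being as extracted.
3. The glossary row contradicts the objectives. Thirty days is the evident intent, and nothing is lost if the analysis paragraph is followed.

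The 77% is a share of time; the documents give no basis for estimating how many bleeds would be misgraded. The consequence is mainly for the final safety comparison and the decision on a larger study, where one bleed in an arm of 25 is 4 percentage points. The effect on modifying or stopping this trial is small. Severity: minor to should-fix.

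**What to change.** Endpoint wording only:

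- **Fatal clause.** In the TIMI table, extend it from 7 days to the 30-day endpoint window.
- **Cut-points.** Check the source table for a lost 'or equal' sign. If there is none, make the two grades contiguous, for example major as a fall of 5 g/dL or more, or hematocrit 15% or more.
- **Window.** Align the glossary row with the Secondary Objectives and the statistical analysis paragraph, state where the window starts, and refer to it in Secondary End Point Assessments and in the Data Monitoring Committee section. Report 0 to 48 hours post procedure as a sub-period if it is of interest.
- **One-week assessment.** Reconcile it with the schedule, either by dropping it or by collecting that information by history at Day 30.

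This adds no visit and no test. Where the 30-day analysis is already followed, the window change adds no post-procedure bleed up to Day 30. The downside is that a few bleeds may be regraded as major, so the criteria will differ slightly from the present table; the report should state the changed wording.

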## LIST OF ABBREVIATIONS

ACE	Asymptomatic Cerebrovascular Event
AE	Adverse Event
AF	Atrial Fibrillation
ASA	Aspirin
DOAC	Direct Oral Anticoagulant
CIED	Cardiac Implantable Electrical Devices
CTCAE	Common Terminology Criteria for Adverse Events
CVA	Cerebrovascular Accident
CVE	Cerebrovascular Events
EP	Electrophysiology
ESR	Expedited Safety Report
FDA	Food and Drug Administration
FSH	Follicle-Stimulating Hormone
GCP	Good Clinical Practice
HCG	Human Chorionic Gonadotropin
HRT	Hormone Replacement Therapy
IB	Investigator Brochure
ICD	Implantable Cardioverter Defibrillator

ICH	International Conference on Harmonisation
IEC	Independent Ethics Committee
IND	Investigational New Drug (Application)
IRB	Institutional Review Board
ISR	Investigator-Sponsored Research
MRI	Magnetic Resonance Imaging
NCI	National Cancer Institute
NIHSS	National Institute of Health Stroke Score
NSAE	Non-Serious Adverse Event
RFA	Radiofrequency Ablation
SAE	Serious Adverse Event
SUSAR	Suspected Unexpected Serious Adverse Reaction
TIA	Transient Ischemic Attack
TIMI	Thrombolysis In Myocardial Infarction
VT	Ventricular Tachycardia
VKA	Vitamin K Antagonist
WOCBP	Women of Child-Bearing Potential

## Attachment A

### Algorithm for subjects who have Cardiac implantable devices and who are undergoing brain MRI examination (as adopted from [2])

#### General:

1. MRI scans will be performed in a 1.5 T scanner.
2. Subjects will undergo interrogation of the device (CIED) before and after the scan by experienced heart rhythm management personnel, outside the MRI room.
3. Patient height and weight will be recorded to determine the specific absorption rate (SAR) levels not to exceed the manufacturer's pre-specified limits, if in case, the parameters, repetition times, number of slices and angle will be changed accordingly.
4. A crash cart and ACLS trained health care professional will be available during the entire procedure.
5. Blood pressure, pulse oximetry and cardiac rhythm will be monitored. If any signs of hemodynamic instability (BP<90/60, HR<40) or ventricular fibrillation the procedure will be stopped and patient will be managed as per the ACLS protocol.

#### Device (CIED) interrogation and monitoring:

1. Device interrogation will include measurements of battery voltage, P- and R-wave amplitudes (if present), and lead impedance and pacing threshold for all leads.
2. Pacing threshold measurements will be performed at 10 beats/min above the programmed pacing rate (if pacemaker dependent) or, 10 beats/min above the patient's intrinsic rate. The pacing rate for testing can be increased by increments of 10 beats/min, if there is insufficient suppression of the patient's underlying rhythm.
3. The pacing rate will gradually be decreased to 40 beats/min, if the patient has an intrinsic rhythm of greater than 40 beats/min, the device will be programmed to pacing and sensing functions disabled (ODO) [Chamber paced-none; Chamber sensed--atria and ventricle; Mode of response -none] or OVO [Chamber paced-none; Chamber sensed-ventricle; Mode of response-none]). The patient will then be observed for 5 minutes before the scan. If symptoms are noted, the pacing function will be reprogrammed to an asynchronous pacing mode (DOO) [asynchronous pacing mode using both atrial and ventricular leads] or (VOO) [asynchronous pacing mode using only the ventricular lead]. If the patient has a device that does not allow permanent reprogramming to an ODO or OVO mode, the patient will be

reprogrammed to an asynchronous mode (DOO or VOO), and the pacing output for all active leads and pulse width will be set to a minimum value. If there is no intrinsic rhythm when the device is reprogrammed to 40 beats/min, the patient will be considered pacemaker dependent, and the device will be programmed to an asynchronous pacing mode (DOO or VOO). The patient will be observed for 5 minutes before the scan to ensure that the asynchronous pacing is well tolerated. If not, the original pacing parameters will be restored and the scan will not be performed.

4. Immediately after the scan, initial device parameters will be restored. Post scan device parameter interrogation will be performed using the pre-scan interrogation protocol. If there is a significant increase in pacing threshold ( $\geq 0.5$  V at 0.4 ms or any increase at a wider pulse width) after the scan compared with before the scan, the pacing output will be increased to maintain a 2- to 2.5-times amplitude safety margin at the physician's discretion. If there is a significant decrease in the P- and R-wave amplitudes, the sensitivities will be adjusted to maintain adequate atrial and ventricular electrocardiogram detection.

**Implantable cardioverter-defibrillator interrogation and programming:**

1. The pacing rate will gradually be decreased to, 40 beats/min. If the patient has an intrinsic rhythm and is asymptomatic, the device will be programmed to no pacing (ODO or OVO). All tachycardia therapy and detection functions will be disabled. The patient will be observed for 5 minutes before the scan. If the patient does not have a stable intrinsic heart rate or symptoms are noted, the patient will be considered pacemaker dependent. Subjects with ICDs who are pacemaker dependent are excluded from the study.

2. Immediately after the scan, all tachycardia therapy and detection functions will be restored. Post scan interrogation will be performed as described earlier for pacemaker Subjects.

3. Subjects with 1 or more parameter changes will be asked to return for 3 follow-up interrogations over a six-month period, which will be scheduled less than 7 days after the procedure, again at 3 months ( $\pm 30$  days) after the MRI procedure, and at 6 months ( $\pm 30$  days) after the MRI procedure. If no parameter changes requiring multiple follow-up visits occur, the patient will require a single-device interrogation between 3 and 6 months ( $\pm 30$  days) after the MRI procedure.

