## **D. Prohibited Treatments and/or Therapies**

- Participation in another investigational study related to oral anticoagulation, drug and/or device intervention.
- Claustrophobic patients
- ICD generator placement before the year 2000
- Has an ICD and is pacing dependent without underlying rhythm upon interrogation at baseline
- Patient has abandoned leads

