### ***Discontinuation of Subjects from Treatment***

Subjects MUST discontinue investigational product (and non-investigational product at the discretion of the investigator) for any of the following reasons:

- Withdrawal of informed consent (subject's decision to withdraw for any reason).
- Any clinical adverse event, laboratory abnormality, or inter-current illness which, in the opinion of the investigator, indicates that continued participation in the study is not in the best interest of the subject.
- Pregnancy
  - Instruct WOCBP to contact the investigator or study staff immediately if they suspect they might be pregnant (eg, missed or late menstrual period) at any time during study participation. Institutional policy and local regulations should determine the frequency of on-study pregnancy tests for WOCBP enrolled in the study.
  - The investigator must immediately notify BMS if a study subject becomes pregnant.
- Loss of ability to freely provide consent through imprisonment or involuntary incarceration for treatment of either a psychiatric or physical (eg, infectious disease) illness.

All subjects who discontinue should comply with protocol-specified follow-up procedures outlined above. The only exception to this requirement is when a subject withdraws consent for all study procedures or loses the ability to consent freely (ie, is imprisoned or involuntarily incarcerated for the treatment of either a psychiatric or physical illness). If a subject withdraws before completing the study, the reason for withdrawal must be documented appropriately.

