## STUDY ASSESSMENTS AND PROCEDURES

### Study Schematic

#### Time and Events Schedule

Procedure	Baseline (Within 30 days of the procedure)	Randomization (Within 48 prior to procedure)	Prior to Procedure (Within 24 hours of procedure)	Day of Procedure	24-48 hours Post- Procedure	Discharge	Day 30 (+/- 7 days) Follow- Up
Eligibility Assessments							
Informed Consent	X						
Medical History	X						
Inclusion/Exclusion Criteria	X						
Study Assessments:							
Physical Examination	X			X	X	X	X
Vital Signs	X		X	X	X	X	X
Adverse Events Assessment	X	X	X	X	X	X	X
Evaluation of Bleeding Events	X		X	X	X	X	X
Laboratory Tests	X						
Pregnancy Test	X						
Ablation Procedure				X			
Device Interrogation			X		X	X	X
Cerebral MRI					X		X
Neurology Evaluation NIHSS			X		X		X
EQ5D Survey			X		X		X
Randomization		X					
Dispense Study Drug				X (3 hours post hemostasis)			
Drug Compliance			X	X	X	X	X

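### Attachment A, read literally, excludes randomised and treated ICD patients from the study on a pacing check made just before a post-ablation MRI

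*Combined protocol and SAP*

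**What the plan says.** The relevant text is spread over several sections of the protocol.

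- **Attachment A, ICD interrogation and programming, item 1.** Pacing is lowered to 40 beats/min and tachycardia functions are disabled. Then: "The patient will be observed for 5 minutes before the scan". The classification follows: "If the patient does not have a stable intrinsic heart rate or symptoms are noted, the patient will be considered pacemaker dependent". The item ends: "Subjects with ICDs who are pacemaker dependent are excluded from the study".
- **Exclusion Criteria, part D.** The entry criterion is: "Has an ICD and is pacing dependent without underlying rhythm upon interrogation at baseline".
- **Cerebral MRI and the Time and Events Schedule.** There is no baseline MRI. The two study scans are after ablation (within 24 hours in one section, 24-48 hours in others) and at about day 30. The randomisation column is headed "Randomization (Within 48 prior to procedure" (no unit printed), so randomisation precedes both scans.
- **Study Design and Duration.** All subjects are followed to 30 days after the procedure.
- **Discontinuation of Subjects from Treatment.** "All subjects who discontinue should comply with protocol-specified follow-up procedures outlined above". The only exceptions are withdrawal of consent for all procedures and loss of the ability to consent freely.
- **Attachment A, general device section.** For a patient who does not tolerate asynchronous pacing before the scan, "the original pacing parameters will be restored and the scan will not be performed". Study status is not mentioned.
- **Sample size.** 52 enrolled, 50 analysed, 25 per arm; "The additional 2 allows for attrition".

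The statistical analysis paragraph names no analysis population and gives no rule for a missing MRI.

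**The concern.** An exclusion triggered by a finding after randomisation and treatment differs in kind from an entry criterion. At the first scan, symptoms or an unstable rhythm could reflect bleeding, a procedural complication or a neurological event. Removal on that basis may be related to the endpoints, and the remaining patients would no longer be the groups that were randomised. Whether symptoms are noted is a judgement, and the documents describe no masking of treatment; only the radiologist reading the scans is blinded.

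The removal would also be wider than its cause. A device problem at the scanner affects the MRI. Symptomatic stroke and TIA, systemic embolism and bleeding can still be observed to day 30. If a site takes the sentence at its word, those outcomes may go uncollected or unanalysed.

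**Working it through.** **1. Order of events.** Randomisation, then ablation, then the first MRI, then the day-30 MRI. The Attachment A check is made just before a scan, and no study scan precedes randomisation. As written, then, the check is reached only by patients already randomised and treated.

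**2. The two definitions side by side.**

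| | Exclusion Criteria, part D | Attachment A, ICD item 1 |
|---|---|---|
| When | Interrogation at baseline | Just before a study MRI |
| Finding | Pacing dependent with no underlying rhythm | No stable intrinsic rate, or symptoms |
| Consequence | Not enrolled | Excluded from the study |

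A patient with an underlying rhythm that is unstable, or who becomes symptomatic when pacing is lowered, passes the first and fails the second. Time can also separate them: the Baseline Visit section accepts an interrogation up to 6 months old, and the first one marked in the schedule is within 24 hours of the procedure. The two windows overlap, so the schedule does not settle whether that interrogation comes before or after randomisation.

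**3. Follow-up after exclusion.** Study Design follows all subjects to 30 days. The discontinuation section requires follow-up with two exceptions, and pacing dependence is neither. Exclusion from the study, in its ordinary sense, would be a third. The discontinuation section is headed as concerning treatment and does not address exclusion after randomisation, so the protocol does not say which text governs.

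**4. Size.**
- Plan's own figure: 2 × 25 + 2 = 52, which reproduces. The allowance is 2/52 = 3.8%.
- One patient in an arm of 25: 1/25 = 4%.
- The documents give neither the proportion with an ICD nor a rate of failing the pre-scan check, so the expected number cannot be computed. For illustration only, let all 52 be exposed with assumed failure rate q. This is an upper bound, because only ICD patients who passed the entry criterion are affected. The chance of exceeding the allowance is P(X ≥ 3) for X ~ Binomial(52, q):

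| Assumed q | Expected, 52 × q | P(X ≥ 3) |
|---|---|---|
| 1% | 0.52 | 1.5% |
| 2% | 1.04 | 8.6% |
| 5% | 2.6 | 48.5% |
| 10% | 5.2 | 90.3% |

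- Hypothetical sensitivity: if an arm had two major bleeds and one of those patients were dropped from the analysis, the rate would move from 2/25 = 8.0% to 1/24 = 4.2%.

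**The case against.** The strongest reply is that the sentence only restates the entry criterion. It is worded as a general statement of status, it gives no withdrawal procedure, and Attachment A is described as adopted from another source. Its device follow-up to six months does not fit a 30-day study, which also suggests imported text. This reading is plausible and may well be what was intended. It does not remove the problem: the definitions differ, and a site working through Attachment A at the scanner would read an instruction to exclude.

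Three stronger readings are tempting, and the documents do not support them.

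- *A reader might infer that these patients' stroke and bleeding outcomes are lost.* No section ends their follow-up or discards recorded events, and Study Design and the discontinuation section point the other way. Loss is a risk created by the wording, not a stated rule.
- *A reader might infer that Attachment A contradicts itself, because the general device section only cancels the scan.* That section is silent on study status and describes a different pathway, so different handling is not in itself a contradiction.
- *A reader might infer that exclusions will exceed the attrition allowance.* That rests entirely on assumed failure rates applied to all 52 patients.

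It is also fair to say that this is a pilot for feasibility and safety, and that the baseline criterion should already remove ICD patients with no underlying rhythm.

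**Conclusion.** The point holds as a conflict in the text with a possible effect on the randomised comparison. Read literally, Attachment A excludes randomised, treated ICD patients on a post-treatment finding, under a definition wider than the entry criterion and at odds with the 30-day follow-up rules. Clinical outcomes may be lost as a result, for reasons that may be related to the endpoints; the documents do not establish that they will be.

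The number affected is unknown. What can be said is that each such patient is 4% of an arm, and that the plan allows for two losses in all. A difference between arms in failing the check is possible but cannot be shown from the documents. The conclusion rests on the order of events and the wording of the two definitions, not on any assumed failure rate.

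**What to change.** Reconcile Exclusion Criteria part D, the discontinuation section and Attachment A, including the definition of pacing dependence. The choice of definition belongs to the clinical investigators. Then state the following.

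- The exclusion in Attachment A applies to eligibility only.
- A randomised patient who meets it at a pre-scan check stays in the study and is followed to day 30.
- That patient is analysed in the randomised arm for symptomatic events, systemic embolism and bleeding. Any MRI not obtained is recorded as missing, with its reason.

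Device handling and the decision whether to scan stay with the clinical team. This point does not ask for the pre-scan pacing check to be moved ahead of randomisation, which would add a device procedure.

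The cost is amendment wording. The downside is that some analysed patients will lack the MRI component.
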